Study Protocol

Official Title: Technology and Emotion Study "TECH-E": Randomized Controlled Trial of MoodRing compared to Usual Care: Mobile Monitoring of Adolescent Depression Phase II

ClinicalTrials.gov ID (NCT number): NCT05376358

Protocol Date: 10/14/2022

Scientific Background

Adolescent depression is increasing and limited numbers access treatment. Almost 12% of adolescents have major depression or dysthymia. A third experience suicidality and 11% attempt suicide; resulting in \$12 billion in hospital costs, but only one-third receive treatment, and initial treatment delays average 10 years.

Screening may identify adolescents at risk for depression, who do not address their symptoms until they are in crisis. To increase detection of depressive symptoms, the US Preventive Service Task Force recommends routine screening for major depressive disorder in adolescents aged 12 to 18 years. For those who are at risk for worsening depression, close follow-up with the primary care provider (PCP) is recommended. Most adolescents will wait to seek medical attention only when symptoms are severe or they are in crisis. Although multiple studies show the benefit of addressing depressive symptoms before they worsen, this is not done in practice due to difficulty and burden in requiring patients to self-report and lack of scheduling and attending frequent follow-up visits.

Frequent, passive symptom monitoring which detects depression could help adolescents monitor their symptoms by employing early self-management interventions and make parents and clinicians aware of symptom worsening to avoid worsened outcomes or a crisis situation. Preliminary studies. In the MONARCA project, Frost, Doryab, et al. developed a smartphone app to provide disease insights by collecting passive data relevant to behavioral trends of bipolar disorder in adults. They found patient mood correlated with physical activity, levels of stress, sleep, and phone use, and that phone call duration, speech analysis, and movement data from smartphones could identify manic and depressive states. Their system recognized bipolar states and transitions between those states with 76% accuracy based on 12 weeks of data with 10 patients. [name] led two rounds of data collection at CMU where cohorts of 180 (Spring 2017) and 270 (Spring 2018) freshmen students were recruited to use AWARE for a semester. Baseline, post surveys, and ecological momentary assessment data were

collected to support and validate the outcome of machine learning models. An analysis of first round data detected post-semester depression among freshmen with accuracy of ~86% and change in severity levels with accuracy of 78.6%. A machine learning pipeline was developed to process data on a sensor by sensor basis to identify the best set of sensors that provide the highest accuracy and the minimal set of features required for accurate inferences above the majority class baselines.

We adapted this data to adolescents and used their data to replicate the analysis, rederiving the algorithms.

We will use the data collected from the first phase to create an application, MoodRing, to provide feedback to adolescents, parents, and clinicians on symptom severity using passive sensing technology, to understand whether this application improves the quality of depression management through increasing the application of self-management activities and utilization of timely engagement with healthcare as well as exchange of passively monitored mood information between adolescents, parents, and providers.

Study Objectives

Evaluate the efficacy of MoodRing in a randomized trial.

PRIMARY: 1) Does MoodRing compared to usual care improve the self-management of depression (i.e. active involvement of adolescent patient in managing their depression)? AT 3 MONTHS

EXPLORATORY:

2) Does MoodRing compared to usual care improve the quality of depression management as measured by:

- a) depression symptom reassessment
- b) medication adherence in those on medication
- c) therapy adherence in those in therapy

3) Does MoodRing compared to usual care result in:

- a) less healthcare utilization
- b) decreased depressive symptoms
- c) improved sleep quality
- d) increased application of self-management activities

3) Is improvement in self-management of depression mediated by perceived severity, social support, self-management knowledge and skills, and self-efficacy?

4) Do healthcare providers, adolescents, parents report satisfaction with MoodRing?

Study Design & Methods

Randomized trial. Study procedures: We will recruit adolescents with a history of depression using similar mechanisms as in the Phase 1 study (IRB protocol #18120176). This will include recruitment through clinical sites at CAYAH (4 clinical sites) and the University of Pittsburgh Research Registry, Pitt+Me, run by the Clinical and Translational Science Institute as well as from the STAR center. Most participants for the Phase 1 study were successfully recruited through the STAR center. We will also recruit using social media advertisements. The research assistant (RA) will screen interested adolescents for meeting inclusion/exclusion criteria – have a prior or present history of depression per self- report and/or clinician diagnosis - and enroll those with a score of at least 5 or higher on the PHQ-9 who do not have active suicidality. Most adolescents recruited from the STAR center will have completed their acute phase of treatment in intensive outpatient treatment and will be receiving outpatient psychotherapy and/or antidepressant management. Adolescents age 12-18 and their parent will be consented for the study and be sent an online survey for baseline measures. Those who complete the baseline measures will then be randomized to receive the MoodRing intervention or treatment as usual and asked to complete data collection at 3 months and 6 months by online survey. Additionally, data will be collected via the electronic health record and from patients' healthcare providers who consent to participate in the study. Randomization: Adolescents will be

randomized at a 1:1 ratio (using randomized block sizes) to MoodRing with feedback to adolescent, parent, and healthcare provider team or to usual care with collection of passive sensing and survey data without the use of the MoodRing app. The randomization tables will be generated by the study statistician.

Eligibility Criteria

Included if

- age 12 -18
- prior or present history of depression per self-report and/or clinician diagnosis
- scores between 5 or higher on PHQ-9 consistent with at least mild symptoms
- read and understand English
- has an Android or iOS smartphone compatible with AWARE APP and access to a smartphone data plan
- currently in United States

Excluded if

- currently actively suicidal (have suicidal thoughts and plan with an intent to act on it)
- plans to travel to countries belonging to the European Union (Austria, Belgium, Bulgaria, Croatia, Cyprus, Czech Republic, Denmark, Estonia, Finland, France, Germany, Greece, Hungary, Ireland, Italy, Latvia, Lithuania, Luxembourg, Malta, The Netherlands, Poland, Portugal, Romania, Slovakia, Slovenia, Spain, Sweden), the

United Kingdom (England, Scotland, Wales, and Northern Ireland), Norway, Iceland, or Lichtenstein in the next 6 months for more than 2 weeks at a time

Parent/Guardian

Included if:

- adolescent qualifies for study and assents to enroll
- understands English
- currently in United States
- has a smartphone device that can download the intervention application

Excluded if:

- If their adolescent child is excluded

Statistical Considerations

The primary outcome is self-management using the Partners in Health Scale which is a continuous scale of self-management knowledge and behavior. <https://www.publish.csiro.au/PY/PY03022> Our planned sample would give us the power to detect a small effect size. For the full sample (N=200): 80% power (alpha=0.05) to detect cohens d = .40. Complete data with 10% dropout (N=180): 80% power (alpha=0.05) to detect cohens d = .42."

Data Analysis: Baseline summary statistics will be displayed. The CONSORT diagram will be completed to ensure reporting transparency. The main outcome for Phase II is self-management of depression. To assess intervention efficacy, the primary approach will be an intent to treat analysis with a mixed model with a random intercept treatment as the effect of interest. Predictors will be treatment, time, and treatment*time interaction. Covariates will be age, history of therapy, and phq9 total score.

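### No rule stops siblings who share a parent from being split across arms, although the parent receives MoodRing; a one-adolescent-per-household exclusion would close this route

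*Combined protocol and SAP*

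**What the plan says.** Study Design & Methods states that adolescents are "randomized at a 1:1 ratio (using randomized block sizes) to MoodRing with feedback to adolescent, parent, and healthcare provider team", against "usual care with collection of passive sensing and survey data without the use of the MoodRing app". On how the allocation list is made, it adds only that "The randomization tables will be generated by the study statistician". No grouping or stratification by household is mentioned.

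Under Eligibility Criteria, none of the adolescent inclusion or exclusion lines concerns other members of the household. Under Parent/Guardian, a parent enters if the "adolescent qualifies for study and assents to enroll" and if the parent "has a smartphone device that can download the intervention application". The only parent exclusion is "If their adolescent child is excluded". Nothing limits a parent to one enrolled child.

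For the provider side, Study Design & Methods lists "recruitment through clinical sites at CAYAH (4 clinical sites", the STAR center, a research registry and social media. It also says that data will come "from patients' healthcare providers who consent to participate in the study".

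**The concern.** Individual randomisation keeps the arms separate only if what is delivered to one participant does not reach another. Here the parent receives feedback as part of the intervention, and the Scientific Background presents exchange of mood information among adolescent, parent and provider as one of the ways MoodRing should work. When two eligible siblings enrol, the same parent can hold the app for one child while the other is a control in the same home. The control arm is kept from using the app, but nothing restricts what a parent already using it may do for the other child.

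If the parent's changed behaviour, or app content shared at home, improved the control sibling's self-management, the difference in Partners in Health scores at 3 months would shrink. The error would run towards a null result.

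**Working it through.** **1. Is there a safeguard?** Four places could hold one:
- adolescent criteria: no household rule;
- parent criteria: the sole exclusion depends on the child's own eligibility;
- randomisation text: individual allocation in blocks, with no household unit;
- analysis text (Statistical Considerations): treatment, time, their interaction, age, therapy history and PHQ-9, with no household term.

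None closes the route.

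**2. How often would a sibling pair be split?** The protocol says that block sizes vary but does not give them, so no single figure can be stated. For two consecutive entries and a fixed block size b, the chance that both fall in one block is (b − 1)/b, and the chance of opposite arms within a block is b/[2(b − 1)]. Across two blocks the chance of opposite arms is 1/2. The total is 1/2 + 1/(2b):
- b = 2: 75%
- b = 4: 62.5%
- b = 6: 58.3%

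Blocking therefore makes a split somewhat more likely than a coin toss for siblings enrolled together.

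**3. The plan's own power figures.** Inputs from Statistical Considerations: alpha 0.05, taken as two-sided because that reproduces the figures, and 1:1 allocation. A two-sample t-test gives:
- 100 per arm, d = 0.40: power 80.4% (plan: 80%)
- 90 per arm, d = 0.42: power 80.0% (plan: 80%)

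Both reproduce, with almost no margin.

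**4. What spillover would do.** Let c be the share of the effect reaching controls, averaged over all controls. The observed effect is d(1 − c). The value of c is an assumption; the documents give none. With 100 per arm and d = 0.40:

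| c | d(1 − c) | power (t-test) |
|---|---|---|
| 0 | 0.40 | 80.4% |
| 5% | 0.38 | 76.2% |
| 10% | 0.36 | 71.7% |
| 20% | 0.32 | 61.5% |

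**5. What the household route could contribute.** With k split pairs among 100 controls, and a share s of the effect reaching each exposed control, c = (k/100) × s. Even at s = 1, reaching c = 10% would need 10 split pairs. With k = 2 and s = 1, c = 2%, d becomes 0.392 and power 78.8%. With k = 2 and s = 0.5, c is 1%. Both k and s are illustrative.

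**The case against.** The strongest reply is that MoodRing feedback is patient-specific. It is built from the adolescent's own sensing data, and nothing in the protocol gives a parent or provider feedback about a control. Only indirect spillover remains, through changed behaviour or sharing at home, and the primary outcome is the adolescent's own self-management, one step further away. This stands. It limits the size of the problem but does not remove the route, because one household can contain both arms.

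A reader might go further and infer any of the following. The documents do not support them.
- *That a control whose parent or provider also uses MoodRing has stopped being a usual-care control.* No feedback about that control is generated for anyone.
- *That shared providers dilute the effect by 10–20%.* Neither the number of trial patients per provider nor any spillover rate is given. Sharing a provider is not the same as receiving the intervention. Registry and social-media recruits may share no provider, and the protocol does not say that the STAR center delivers its recruits' later outpatient care. Some provider-level overlap is an accepted trade-off of individual randomisation.
- *That correlation between siblings invalidates the primary test.* Under individual randomisation siblings' allocations are uncorrelated, or slightly negatively correlated under blocking, so ignoring it does not inflate type I error on average. The level of the random intercept is also not stated.

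**Conclusion.** The point holds for households. Adolescents are allocated one at a time, the parent is a recipient of the intervention, and no eligibility or allocation rule keeps siblings out of opposite arms. If benefit passes to a control sibling, the 3-month difference is biased towards zero.

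The effect on the primary result is probably small, because few sibling pairs are likely, though their number is not given. The fall in power from about 80% to 72% or 61% is only an illustration at assumed average spillovers of 10% and 20%; it is not an estimate for this trial. The plan's power arithmetic is correct. The case for the change rests on its low cost, not on a demonstrated loss.

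**What to change.** Add one line to the adolescent exclusion criteria: another adolescent from the same household is already enrolled. The cost is the loss of an occasional second sibling. The sample size and primary analysis stay as they are.

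Optionally, record each participant's treating provider and clinic before allocation, in both arms. The report can then state how many controls shared a provider with a MoodRing participant, and a null result can be read with that in mind. This costs one or two baseline fields and should stay descriptive.

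A comparison of exposed with unexposed controls should not be added. Exposure would be confounded with recruitment source. With about 90 control completers split 45/45 (an assumed split), the detectable difference at 80% power is about d = 0.60. A 10–20% spillover of d = 0.40 is only 0.04–0.08, for which power would be about 5–7%. A flat result would reassure falsely, and a difference could not be interpreted.

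### Does calling the detectable effect "small" when the plan's own figures are d = 0.40 and 0.42 require a change to the power statement?

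*Combined protocol and SAP*

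**What the plan says.** The power statement is in Statistical Considerations. It begins with a verbal summary, "Our planned sample would give us the power to detect a small effect size", and then gives two sets of figures: "For the full sample (N=200): 80% power (alpha=0.05) to detect cohens d = .40" and "Complete data with 10% dropout (N=180): 80% power (alpha=0.05) to detect cohens d = .42".

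The section does not say what it means by small. It also does not name the test, the sidedness or the time point behind the calculation.

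The outcome is the Partners in Health Scale, described as continuous; no standard deviation or target difference in scale points is given. Allocation is 1:1 (Study Design & Methods), and the primary objective is placed at 3 months (Study Objectives). The planned analysis is a random-intercept mixed model with treatment, time and their interaction, and "Covariates will be age, history of therapy, and phq9 total score".

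**The concern.** The plan expresses its effects as Cohen's d, so a reader will naturally apply Cohen's labels: 0.2 small, 0.5 medium. On that scale 0.40 and 0.42 are about twice the small value. The verbal summary and the numbers after it then appear to disagree, and the summary errs in the favourable direction.

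The word has some potential weight because the documents give no target difference on the outcome scale, so it is their only verbal description of sensitivity. If the trial returned a null result, someone relying on that word alone might conclude that a small benefit had been ruled out. A design with 80% power at 0.40 would usually miss an effect of 0.2.

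**Working it through.** **Inputs.** From the documents: N = 200 (100 per arm) and N = 180 (90 per arm, since 200 × 0.90 = 180), 1:1 allocation, alpha 0.05, power 80%. Effects are in SD units, so SD = 1. Assumptions: a two-sided test, and d = 0.2 as the meaning of small. Neither is stated in the plan.

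**Step 1: reproduce the plan's figures.** With n per arm, the normal approximation to the detectable effect is d = (1.960 + 0.842) × √(2/n).

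- n = 100: 2.802 × 0.1414 = 0.396. The exact noncentral t gives 0.398. Stated: 0.40.
- n = 90: 2.802 × 0.1491 = 0.418. The exact noncentral t gives 0.420. Stated: 0.42.

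Both reproduce. A one-sided 0.05 test would give 0.353 and 0.372, so the calculation behind the plan was evidently two-sided.

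**Step 2: power at the conventional small effect, same test.** Power ≈ Φ(d × √(n/2) − 1.960).

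| | N = 200 | N = 180 |
|---|---|---|
| d × √(n/2) at d = 0.2 | 0.2 × 7.071 = 1.414 | 0.2 × 6.708 = 1.342 |
| Power at d = 0.2, normal | 29.3% | 26.8% |
| Power at d = 0.2, noncentral t | 29.1% | 26.6% |
| Power at d = 0.3, noncentral t | 56.0% | 51.7% |

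Reaching 80% at d = 0.2 would need about 394 analysed per arm.

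**Step 3: does the planned model change the picture?** The documents give no correlation for the outcome, so this is a sensitivity range over an assumed r. All figures are power at d = 0.2 by the normal approximation: the effect is divided by the residual SD shown and put into the Step 2 formula.

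| Contrast | Residual SD | r = 0.5 (N = 200 / 180) | r = 0.7 | r = 0.8 |
|---|---|---|---|---|
| 3 months, adjusted for a baseline predictor | √(1 − r²) | 37% / 34% | 51% / 47% | 65% / 61% |
| Change from baseline to 3 months | √(2(1 − r)) | 29% / 27% | 45% / 41% | 61% / 56% |
| Mean of 3 and 6 months, baseline-adjusted, equal correlations | √((1 + r)/2 − r²) | 52% / 48% | 65% / 61% | 79% / 75% |

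The answer depends on the contrast and on r. None of these cases reaches 80% at d = 0.2. The change contrast equals the unadjusted test at r = 0.5 and is weaker below that. The unadjusted 27–29% is therefore not the power of the planned analysis, and the documents do not allow that power to be computed.

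**Step 4: what depends on the word.** The sample size, the two detectable effects, alpha, the dropout allowance and the analysis model are all stated without reference to it. Removing it leaves each of them as it is.

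**The case for a change.** The strongest case for acting is that the sentence is inaccurate under the most natural reading and that correcting it costs one line. Reading small as the whole band from 0.2 to just under 0.5 does not fully rescue it: the unadjusted design reaches 80% only in the upper part of that band and has between 27% and 56% power for effects of 0.2 to 0.3. Nor does the mixed model rescue it under the correlations tried above.

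The arithmetic in that case stands, and the wording is loose. The claim that the loose wording misleads in practice does not stand. The sentence attaches no power level or effect size to the word; the sentences that do so come directly after it and are right. A reader interpreting a null result would use those figures and, above all, the confidence interval from the trial.

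A rewritten sentence could also bring in problems of its own. Describing the calculation as a two-sided, two-sample comparison at 3 months would present inferences as plan facts. Writing in 27–29% power at d = 0.2 would attach an unadjusted figure to an adjusted repeated-measures analysis. Calling the effect small-to-medium would replace one undefined label with another.

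**Conclusion.** No change to the plan is needed. Every number in the power statement is correct: 80% power at d = 0.40 with 200 participants and at d = 0.42 with 180, reproduced as 0.398 and 0.420. The only fault is an adjective, and it is a fault only if small means d = 0.2, a convention the documents do not adopt. On that reading the detectable effect is about twice small, and an unadjusted two-sided t-test would have 29.1% (N = 200) or 26.6% (N = 180) power at 0.2.

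This is a clerical looseness that the following sentences already put right. Correcting it would alter no sample size, analysis, error rate or conclusion. Anyone citing the trial's sensitivity should cite the d values, not the label. The conclusion rests on a two-sided test, which is inferred because only that reproduces the stated figures, and it does not depend on any assumed correlation.

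### A random intercept is the only dependence term named for three survey visits, so the standard error of the 3-month effect rests on a variance condition that the plan does not discuss

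*Combined protocol and SAP*

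**What the plan says.** Under Statistical Considerations, the Data Analysis paragraph gives the primary analysis as an "intent to treat analysis with a mixed model with a random intercept". It continues: "Predictors will be treatment, time, and treatment*time interaction". It then adds: "Covariates will be age, history of therapy, and phq9 total score". The baseline Partners in Health score is not among these covariates.

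Under Study Design & Methods, participants will "be sent an online survey for baseline measures" and, after randomization, are "asked to complete data collection at 3 months and 6 months by online survey". Study Objectives ties the primary question to one of these visits: "active involvement of adolescent patient in managing their depression)? AT 3 MONTHS".

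Two statements bear on which contrast is meant. The analysis sentence has "treatment as the effect of interest", and the power statement reads "Complete data with 10% dropout (N=180): 80% power (alpha=0.05) to detect cohens d = .42".

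The plan does not state which visits are outcome rows, whether time is categorical or linear, the residual covariance, the type of standard error, or which coefficient or contrast is the primary test.

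**The concern.** Three outcome rows per participant is the natural reading, though it is not stated. Surveys occur at three points, time and its interaction with treatment are predictors, and the baseline outcome score is not a covariate.

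A random intercept with independent residuals imposes one variance at every visit and one correlation between every pair of visits. Each 3-month contrast then borrows its SE from an average over visits or pairs of visits. If the 3-month quantity is not average in that sense, the primary confidence interval has the wrong width and the test does not have its nominal 5% level.

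Both directions are plausible. Baseline is measured before randomization and both follow-ups after it, so the two follow-ups may resemble each other more than either resembles baseline. Alternatively, correlation may simply fall with the time between visits.

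**Working it through.** **Inputs from the documents.** Visits at 0, 3 and 6 months; 1:1 allocation; alpha 0.05; N = 200, or 180 after 10% dropout; d = 0.40 and 0.42. No SD or between-visit correlation is given. Every correlation and SD ratio below is an assumption, listed in the order 0-3 / 3-6 / 0-6 months.

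**The plan's own figure.** A two-sided, two-sample t test gives 80.4% power at d = 0.40 with 100 per arm, and 80.0% at d = 0.42 with 90 per arm. The stated 80% reproduces. It uses no repeated-measures correlation, so this point does not touch it.

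**Change from baseline to 3 months.** For three complete visits, the within-person sum of squares equals one third of the sum of the three squared pairwise differences. With categorical time and treatment-by-time terms, the residual variance therefore estimates half the average pairwise change variance. The model-based variance of any two-visit change is then (V03 + V36 + V06)/3, whatever V03 itself is. Hence:

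- k = model SE / true SE = sqrt(average V / V03). With equal visit variances this is sqrt((1 − mean r)/(1 − r03)).
- Type I error = 2 × (1 − Φ(1.96k)).
- True SE in SD units, 90 per arm = sqrt(4(1 − r03)/90).
- Power at d = 0.42 = Φ(0.42/SE − 1.96) with the true SE, and Φ(0.42/SE − 1.96k) with the model SE.

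Worked case 0.7/0.7/0.5: mean r = 0.633; k = sqrt(0.367/0.300) = 1.106; type I error 3.0%; SE = sqrt(1.2/90) = 0.1155. Power falls from 95.3% to 92.9%, and the 95% half-width rises from 0.226 to 0.250 SD.

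| Assumed r | k | Type I error | Power, true SE → model SE |
|---|---|---|---|
| 0.6/0.6/0.6 | 1.00 | 5.0% | 88.3% → 88.3% |
| 0.55/0.7/0.4 | 1.00 | 5.0% | unchanged |
| 0.6/0.6/0.5 | 1.041 | 4.1% | 88.3% → 86.6% |
| 0.6/0.6/0.36 | 1.095 | 3.2% | 88.3% → 84.2% |
| 0.7/0.7/0.5 | 1.106 | 3.0% | 95.3% → 92.9% |
| 0.5/0.5/0.25 | 1.080 | 3.4% | 80.4% → 75.8% |
| 0.5/0.7/0.45 | 0.949 | 6.3% | SE too small |
| 0.4/0.7/0.4 | 0.913 | 7.4% | SE too small |

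With equal visit variances, the sign depends only on whether r03 lies above or below the mean of the three correlations. The 0.55/0.7/0.4 row shows that unequal correlations need not cause any distortion.

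**Between-arm difference at 3 months.** Here k = sqrt(average visit variance / 3-month variance).

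- Equal variances: k = 1.
- SD 20% larger at both follow-ups: k = sqrt(1.293/1.44) = 0.948, type I error 6.3%.
- SD 20% larger at baseline: k = sqrt(1.147/1) = 1.071, type I error 3.6%.

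**Numerical checks.** In single REML fits, the random-intercept SE matched the average-pairwise SE to four decimals. Against the SE of the 0-3 change itself it was 0.1273 versus 0.1092 (0.7/0.7/0.49) and 0.1308 versus 0.1462 (0.5/0.8/0.5). Simulation with 90 per arm and 40,000 replicates gave these random-intercept type I errors for the change:

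- 0.6/0.6/0.5: 4.3%
- 0.6/0.6/0.36: 3.1%
- 0.7/0.7/0.5: 2.9%
- 0.5/0.7/0.45: 6.4%
- 0.4/0.7/0.4: 7.4%
- 0.55/0.7/0.4: 5.1%

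An unstructured covariance gave 4.7% to 5.3% in every scenario.

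**The case against.** The strongest reply is that the defect needs several choices the plan does not make: three outcome rows, categorical time, model-based SEs with independent residuals, and a 3-month quantity whose variance is not average. Naming a random intercept does not exclude a residual structure or a robust variance. The wording on treatment as the effect of interest, the two-sample power statement and the 3-month objective all fit a between-arm difference at 3 months. That contrast is undistorted if variances are equal across visits. A primary model with baseline and 3 months only would also be compatible with the objective, and then the change is undistorted. All of this stands, and it is why the point is conditional. It does not remove the point, because the treatment-by-time term keeps the change contrast open and each contrast has its own unexamined variance condition.

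It is also fair to say that the choice of contrast matters more than the covariance. With correct SEs, the change test at d = 0.42 and 90 per arm has power of about 73%, 80.4%, 88.3% and 95.3% at r03 = 0.4, 0.5, 0.6 and 0.7, against about 80% for the level test. This too stands, and the fix must settle the contrast as well as the covariance.

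A reader might infer that the interval is too wide whenever correlation falls with time between visits. The calculations do not support that: in 0.5/0.7/0.45 the six-month-lag correlation is the lowest of the three, yet the interval is too narrow. A reader might also infer that the plan's primary test is shown to be invalid. The documents do not fix the rows, the contrast or the correlations, so they cannot show that.

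**Conclusion.** The concern holds in conditional form. On a three-row, categorical-time reading with model-based SEs, the plan leaves the SE of its 3-month effect resting on a variance condition that it neither states nor checks. The condition is V03 equal to the average pairwise change variance for the change, and 3-month variance equal to the average visit variance for the level difference.

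The direction cannot be known from the documents. Over the tabulated patterns, type I error for the change runs from about 3% to 7%, and where the SE is too large the power loss is about 2 to 5 points. These are illustrations and not bounds: 0.5/0.8/0.5 would give k = sqrt(0.4/0.5) = 0.894 and 8.0%.

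The algebra is exact for complete data and approximate with the planned 10% dropout. A linear time slope would have a different condition. A time-varying PHQ-9 covariate would change the residual covariance, and the plan does not say whether PHQ-9 is baseline only. The harm is moderate, and the stated sample size is unaffected.

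**What to change.** In the Data Analysis paragraph, state that baseline, 3 and 6 months are the outcome rows of the primary model. Treat time as categorical, and use an unstructured within-person covariance fitted by REML with Kenward-Roger degrees of freedom. If that does not converge, fall back to the random intercept with a sandwich variance.

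Name one primary 3-month contrast explicitly. It should be either the treatment-by-time change from baseline to 3 months or, with a common baseline mean across arms, the between-arm difference at 3 months. If the change is chosen, restricting the primary model to baseline and 3 months would also remove the distortion.

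The cost is plan wording and four extra covariance parameters (six instead of two), which is negligible with about 180 participants. No new data and no change in sample size are needed.

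### The primary question is the arm difference at 3 months, but the primary analysis names a treatment effect beside a treatment-by-time interaction without tying it to 3 months

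*Combined protocol and SAP*

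**What the plan says.** Study Objectives has one primary question, whether MoodRing improves self-management relative to usual care, and gives it a time: "active involvement of adolescent patient in managing their depression)? AT 3 MONTHS". Study Design & Methods has surveys at baseline (before randomization), 3 months and 6 months.

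Statistical Considerations names the outcome without a visit: "The primary outcome is self-management using the Partners in Health Scale". The Data Analysis paragraph repeats this, again without a visit: "The main outcome for Phase II is self-management of depression". It continues "To assess intervention efficacy, the primary approach will be an intent to treat analysis". The model it names for this purpose is "a mixed model with a random intercept treatment as the effect of interest". The fixed effects follow: "Predictors will be treatment, time, and treatment*time interaction". Then: "Covariates will be age, history of therapy, and phq9 total score". The baseline Partners in Health score is not in that list.

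The power statement gives 80% at alpha 0.05 for d = .40 with N=200. For N=180, after 10% dropout, it gives "80% power (alpha=0.05) to detect cohens d = .42".

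**The concern.** In a model with a treatment-by-time interaction, the treatment effect has no fixed meaning until the visits and the coding of time are set. The plan leaves open which visits are outcome rows, whether time is categorical or linear, its reference point, which contrast decides the trial, and whether the baseline score is an outcome, a covariate or unused.

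Some choices give the 3-month difference. Others give an average over visits, which answers a different question unless the effect follows a particular course. At stake is whether the primary test answers the primary objective, and whether that test is fixed before the data are seen.

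**Working it through.** **Stated power.** For a two-sided, two-arm comparison at one visit with SD 1, the noncentrality is d / sqrt(2/n), with n per arm.
- N=200, d=.40: 0.40 / sqrt(2/100) = 2.83, df 198, power 80.4%.
- N=180, d=.42: 0.42 / sqrt(2/90) = 2.82, df 178, power 80.0%.

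Both stated figures reproduce. One-sided testing gives about 88% and does not match.

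**Inputs.** From the plan: 1:1 allocation, so 180/2 = 90 per arm; alpha 0.05; d = .42; visits at 0, 3 and 6 months. Assumed, because the plan gives no values: complete data, equal variances, the same within-person correlation r between any two visits (r = 0.3, 0.5, 0.7), covariates that do not change precision, and the effect profiles below. Randomization makes the expected baseline difference zero.

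**Method.** Each reading is a contrast c of the arm differences at 0, 3 and 6 months. Its expected value is c'd. Its variance is (2/90) c'Sc, where S has 1 on the diagonal and r elsewhere. Power is from the two-sided noncentral t with 178 df.

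| Reading | c | c'Sc |
|---|---|---|
| 3-month difference | (0, 1, 0) | 1 |
| Change from baseline to 3 months | (-1, 1, 0) | 2(1 - r) |
| Average of 3 and 6 months | (0, 1/2, 1/2) | (1 + r)/2 |
| Average of all three visits | (1/3, 1/3, 1/3) | (1 + 2r)/3 |

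Example, average of 3 and 6 months, r = 0.5, effect 0.42 at 3 months and 0 at 6: expected value 0.21, variance (2/90)(0.75) = 0.0167, SE 0.129, noncentrality 0.21/0.129 = 1.63, power 37%.

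**Rejection rates (%) for r = 0.3/0.5/0.7.** Profiles are the true differences at 3 and 6 months.

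| Reading | 0.42, 0.42 | 0.42, 0.21 | 0.42, 0 | 0, 0.42 |
|---|---|---|---|---|
| 3-month difference | 80/80/80 | 80/80/80 | 80/80/80 | 5/5/5 |
| Change to 3 months | 66/80/95 | 66/80/95 | 66/80/95 | 5/5/5 |
| Average of 3 and 6 | 94/90/86 | 74/68/63 | 41/37/33 | 41/37/33 |
| Average of all three | 73/63/55 | 48/40/35 | 25/21/18 | 25/21/18 |

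**When the readings agree.**
- With 3- and 6-month outcomes and 3 months as reference, the treatment term is exactly the 3-month difference.
- Change from baseline has the same expected value as the 3-month difference in every profile and differs only in precision.
- The two-visit average has the same expected value only if the effects at 3 and 6 months are equal.
- The three-visit average has it only if the differences grow in a straight line: (0 + d + 2d)/3 = d. Under a sustained 0.42 it is 0.84/3 = 0.28.
- Linear time with its zero at 3 months, fitted to all three equally spaced visits, gives that same three-visit average. Moving the zero point is therefore not enough in that model; time should be categorical.

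**Using the baseline score.** Adjusting the 3-month difference for it multiplies the variance by 1 - r², that is 0.91/0.75/0.51. Noncentrality becomes 2.95/3.25/3.95 and power 84/90/98% (df 177), with the same target.

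**Simulation.** Random-intercept models with three covariates that had no effect on the outcome were fitted to 4,000 simulated trials per scenario (Monte Carlo SE at most 0.8 points). For the sustained effect, the 3-month difference gave 79.4/78.7/80.0% and the 3- and 6-month average 92.8/89.5/85.8%. With the effect only at 6 months, they gave 4.6/5.1/5.8% and 39.7/37.0/32.2%.

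**The case against.** The best defence is that Study Objectives and Statistical Considerations should be read together. The only primary objective carries a 3-month time point, and the power statement fits a single visit. On that view the estimand is known and only the model term is unnamed. The plan never mentions averaging over visits, and the lowest figures need an effect that vanishes by, or first appears at, 6 months, which nothing in the documents suggests. If the effect is sustained, the 3- and 6-month average has the same expected value as the 3-month difference and more power.

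Most of this stands. It limits the point to a named effect that is not tied to the stated objective; it does not remove the point. The analysis paragraph defines the test, and nothing in it links the treatment term to 3 months.

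Three stronger inferences are tempting and are not supported:
- *That the plan tests the baseline difference.* With baseline as reference, the main-effect coefficient would be the baseline difference and would reject 5% of the time. The plan does not set that coding, and a test of baseline balance contradicts the stated aim of assessing efficacy.
- *That change from baseline is a different question.* Under randomization it has the same expected value at 3 months.
- *That the trial is underpowered.* The stated power is correct for the 3-month difference.

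**Conclusion.** The point holds as under-specification with a possible mismatch, and should be fixed. That no model term is tied to 3 months is certain from the text. That the 3-month difference was intended is probable. Averaging is a possible reading, not a demonstrated one.

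If the 3- and 6-month average were used, the consequence would run from a gain over the 80% of the 3-month test (sustained effect), through a modest loss (effect halved by 6 months), to a loss of about half or more (effect gone by 6 months). An effect confined to 6 months would give a positive primary test in a third or more of trials although the 3-month difference is zero. These sizes depend on the assumed correlations and profiles; the mismatch between objective and named effect does not.

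**What to change.** In the Data Analysis paragraph, replace the phrase that makes treatment the effect of interest with: *The primary test is the model-based MoodRing minus usual care difference in Partners in Health score at 3 months (two-sided alpha 0.05), with categorical time.* State which visits are outcome rows. Label any 6-month difference as not primary.

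If the Partners in Health score is in the baseline survey, which the documents do not itemise, use it. Either enter it as a covariate with the 3- and 6-month scores as outcomes, or keep it as an outcome row with the arms constrained equal at baseline. Both keep the 3-month target and raise power as shown above. If it is not collected at baseline, the named contrast and the outcome visits are enough.

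The cost is revised analysis wording and, where the baseline score is used, one added covariate or one constraint. This is a small change to the model as well as to its description. Sample size, visits and primary outcome stay as they are.
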